9.2.1. Inclusion Criteria

Patients must meet all of the following inclusion criteria to be eligible for inclusion in the study:

- At least 1 observed prescription claim or medical claim for elranatamab or teclistamab in the
 dataset between August 14, 2023, and the most current date of data available. The index date will
 be the date of an individual's first claim. Patients who have received teclistamab before the
 August 14, 2023, date will require a period (i.e., 6 or 12 months) without a claim for teclistamab.
- 2. Age 18 or older on index date

- 3. Diagnosis of RRMM (defined as MM) any time prior to index date
- 4. At least 180 days of continuous closed-claims medical and pharmacy enrollment prior to index (inclusive) and 30 days post-index

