Exploratory Obj 1	Hypogammaglobuli nemia ¹	Medical claim with an ICD-10 code in the inpatient, non-IP, or pharmacy setting for hypogammaglobulinemia (dichotomous)	Index date to end of follow-up, where follow-up will be based on last dose of elranatamab or teclistamab (e.g., 14 days after last recorded dose or 90 days after last recorded dose).
Exploratory Obj 1	Hypophosphataemia	Medical claim with an ICD-10 code in the inpatient, non-IP, or pharmacy setting for hypophosphatemia (dichotomous)	Index date to end of follow-up, where follow-up will be based on last dose of elranatamab or teclistamab (e.g., 14 days after last recorded dose or 90 days after last recorded dose).
Exploratory Obj 1	Hypokalaemia ¹	Medical claim with an ICD-10 code in the inpatient, non-IP, or pharmacy setting for hypokalemia (dichotomous)	Index date to end of follow-up, where follow-up will be based on last dose of elranatamab or teclistamab (e.g., 14 days after last recorded dose or 90 days after last recorded dose).
Exploratory Obj 1	Hepatotoxicity ¹	Medical claim with an ICD-10 code in the inpatient, non-IP, or pharmacy setting for hepatotoxicity (dichotomous)	Index date to end of follow-up, where follow- up will be based on last dose of elranatamab or teclistamab (e.g., 14 days after last recorded dose or

			90 days after last recorded dose).
Exploratory Obj 1	Renal failure ²	Medical claim with an ICD-10 code in the inpatient, non-IP, or pharmacy setting for renal failure (dichotomous)	Index date to end of follow-up, where follow-up will be based on last dose of elranatamab or teclistamab (e.g., 14 days after last recorded dose or 90 days after last recorded dose).
Exploratory Obj 1	Peripheral neuropathy ¹	Medical claim with an ICD-10 code in the inpatient, non-IP, or pharmacy setting for peripheral neuropathy (dichotomous)	Index date to end of follow-up, where follow-up will be based on last dose of elranatamab or teclistamab (e.g., 14 days after last recorded dose or 90 days after last recorded dose).
Exploratory Obj 1	Arthralgia ³	Medical claim with an ICD-10 code in the inpatient, non-IP, or pharmacy setting for arthralgia (dichotomous)	Index date to end of follow-up, where follow-up will be based on last dose of elranatamab or teclistamab (e.g., 14 days after last recorded dose or 90 days after last recorded dose).

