Exploratory Obj 1	Other pneumonia ²	Medical claim with an ICD-10 code in the inpatient, non-IP, or pharmacy setting for pneumonia other than adenoviral or cytomegaloviral pneumonia (dichotomous)	Index date to end of follow-up, where follow-up will be based on last dose of elranatamab or teclistamab (e.g., 14 days after last recorded dose or 90 days after last recorded dose).
Exploratory Obj 1	Upper respiratory tract Infection ²	Medical claim with an ICD-10 code in the inpatient, non-IP, or pharmacy setting for upper respiratory tract infection (dichotomous)	Index date to end of follow-up, where follow-up will be based on last dose of elranatamab or teclistamab (e.g., 14 days after last recorded dose or 90 days after last recorded dose).
Exploratory Obj 1	Sepsis ²	Medical claim with an ICD-10 code in the inpatient, non-IP, or pharmacy setting for sepsis (dichotomous)	Index date to end of follow-up, where follow-up will be based on last dose of elranatamab or teclistamab (e.g., 14 days after last recorded dose or 90 days after last recorded dose).
Exploratory Obj 1	Cytomegaloviral infection ²	Medical claim with an ICD-10 code in the inpatient, non-IP, or pharmacy setting for cytomegaloviral infection (dichotomous)	Index date to end of follow-up, where follow- up will be based on last dose of elranatamab or teclistamab (e.g., 14 days after last recorded dose or

			90 days after last recorded dose).
Exploratory Obj 1	PJP ²	Medical claim with an ICD-10 code for PJP (dichotomous)	Index date to end of follow-up, where follow-up will be based on last dose of elranatamab or teclistamab (e.g., 14 days after last recorded dose or 90 days after last recorded dose).
Exploratory Obj 1	Hepatitis C ²	Medical claim with an ICD-10 code in the inpatient, non-IP or pharmacy setting for hepatitis C (dichotomous)	Index date to end of follow-up, where follow-up will be based on last dose of elranatamab or teclistamab (e.g., 14 days after last recorded dose or 90 days after last recorded dose).
Exploratory Obj 1	Hepatitis B ²	Medical claim with an ICD-10 code in the inpatient, non-IP or pharmacy setting for hepatitis B (dichotomous)	Index date to end of follow-up, where follow-up will be based on last dose of elranatamab or teclistamab (e.g., 14 days after last recorded dose or 90 days after last recorded dose).

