Exploratory Obj 1	Other infectious hepatitis ²	Medical claim with an ICD-10 code in the inpatient, non-IP or pharmacy setting for infectious hepatitis (other than hepatitis B or C) (dichotomous)	Index date to end of follow-up, where follow-up will be based on last dose of elranatamab or teclistamab (e.g., 14 days after last recorded dose or 90 days after last recorded dose).
Exploratory Obj 1	Helicobacter pylori ²	Medical claim with an ICD-10 code in the inpatient, non-IP or pharmacy setting for helicobacter pylori (dichotomous)	Index date to end of follow-up, where follow-up will be based on last dose of elranatamab or teclistamab (e.g., 14 days after last recorded dose or 90 days after last recorded dose).

Exploratory Obj 1	Candida esophagitis ²	Medical claim with an ICD-10 code in the inpatient, non-IP or pharmacy setting for candida esophagitis (dichotomous)	Index date to end of follow-up, where follow-up will be based on last dose of elranatamab or teclistamab (e.g., 14 days after last recorded dose or 90 days after last recorded dose).				
Exploratory Obj 1	Urinary tract infection ²	Medical claim with an ICD-10 code in the inpatient, non-IP or pharmacy setting for a urinary tract infection (dichotomous)	Index date to end of follow-up, where follow-up will be based on last dose of elranatamab or teclistamab (e.g., 14 days after last recorded dose or 90 days after last recorded dose).				
Exploratory Obj 1	Time to infection onset	Time in days from index date to first infection for the following infections:	Index date until censor				
Effectiveness	Effectiveness						
Exploratory Obj 2	os	Time (in months) from index date until date of death (continuous)	Index date until censor				
Exploratory Obj 2	TTNT/D	Time (in months) from index date until the date of the next treatment (CAR-T, BsABs, bendamustine or belantamab) or death (continuous)	Index date until censor				

- 1. Variable will be measured as incident and prevalent. Incident cases have 30-day washout period applied
- 2. Variable will be measured as incident and prevalent. Incident cases have 60-day washout period applied
- 3. Variable will be measured as incident and prevalent. Incident cases have 14-day washout period applied

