9.7.6. Tolerability

The prevalence and incidence for each adverse event (Table 3) will be estimated. All prevalence and incidence estimates will be reported as a percent with corresponding 95% CIs.

Prevalance =
$$(\frac{No.\ of\ patients\ with\ an\ event}{Total\ number\ of\ patients\ in\ the\ cohort})\ x\ 100$$

For the incidence analysis, only patients who did not have the event prior to their index date will be included. The length of the washout is dependent on the outcome (see Table 3).

$$Incidence = \left(\frac{\text{No. of patients with an event that did not have an event in baseline}}{\text{Total number of patients in the cohort}}\right) x \ 100$$

PFIZER CONFIDENTIAL

Patients will be assessed over two time periods: from the index date until 14 days or 90 days after their last administration of the index medication.

Additionally, the time to infection onset will be assessed using unadjusted Kaplan-Meier methods. The median time to event in days will be reported along with the IQR. The 95% CIs for the median time to event will be calculated using log-log transformation.

Patients will be censored at the earliest of death, next treatment (CAR-T, BsABs, bendamustine or belantamab), the end of part A or B continuous closed-claim coverage, or the end of data.

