	Clinical, Adverse event		E13.41, G57.70, G57.71, G57.72, G57.73, G59, G57.80, G57.81, G57.82, G57.83, G58.8, G58.9, G64., G61.0, M05.50, M05.511, M05.512, M05.519, M05.521, M05.522, M05.529, M05.531, M05.532, M05.539, M05.541, M05.542, M05.549, M05.551, M05.552, M05.559, M05.551, M05.552, M05.559, M05.571, M05.572, M05.579, M05.59, E08.40, E08.42, E09.40, E09.42, E10.40, E10.42, E11.40, E11.42, E13.40, E13.42, G13.0, G13.1, A36.83, A52.15, G63, M34.83, G62.1, G61.1, G62.0, G62.2, G62.82, G61.81, G62.81, G61.89, G62.89, G61.9, G62.9, H46.3, M54.10, M54.18, M79.2, R20.0, R20.1, R20.2, R20.3, R20.8, R20.9
Any infection	Baseline characteristic - Clinical	Claims data	An ICD-10 Diagnosis Code for any of the following types of infections. See the rows below for codes for each infection type. COVID-19, Adenoviral pneumonia, Cytomegaloviral pneumonitis, Other Pneumonia, Upper respiratory tract infection, Sepsis, Cytomegaloviral infection, Pneumocystis jiroveci pneumonia (PJP), Hepatitis C, Hepatitis B, Other infectious hepatitis, Helicobacter pylori, Candida esophagitis, Urinary tract infection
Use of intravenous anti- infective	Baseline characteristic - Clinical	Claims data	See "Antivirals" and "Antibiotics" above
Neutropenia	Baseline characteristic - Clinical, Adverse event	Claims data	ICD-10 Diagnosis: D70x
Hypercalcemia	Baseline characteristic - Clinical	Claims data	ICD-10 Diagnosis: E83.52
Hypoxia	Baseline characteristic - Clinical, Adverse event	Claims data	ICD-10 Diagnosis: J96.20, J96.11, J96.90, J96.01, J96.00, J96.10, J96.21, J96.91, I27.23, R09.02
Hepatotoxicity	Baseline characteristic - Clinical, Adverse event	Claims data	ICD-10 Diagnosis: K71.x
Renal failure	Baseline characteristic -	Claims data	ICD-10 Diagnosis: N17x, N18x, N19x, R34x, T82.4, Z49.02, Z99.2

	Clinical, Adverse event		
Amyloidosis	Baseline characteristic - Clinical	Claims data	ICD-10 Diagnosis: E85.4x, E85.8x, E85.9x
Hypertension	Baseline characteristic - Clinical	Claims data	ICD-10 Diagnosis: I10x-I15x, I16x
Extramedullary disease	Baseline characteristic - Clinical	Claims data	ICD-10 Diagnosis: C90.2x
CCI score	Baseline characteristic - Clinical	Claims data	See components below
Myocardial infarction	Baseline characteristic - Clinical	Claims data	ICD-10 Diagnosis: I21.x, I22.x, I25.2
Congestive heart failure	Baseline characteristic - Clinical	Claims data	ICD-10 Diagnosis: I11.0, I13.0, I13.2, I25.5, I42.0, I42.5, I42.6, I42.7, I42.8, I42.9, I43.x, I50.x, P29.0

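### Washouts of 30 and 60 days let pre-existing neuropathy, renal failure and hepatitis B/C count as incident when their code lists include chronic states

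*Protocol*

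**What the plan says.** Section 9.7.6 (Tolerability) states that for incidence "only patients who did not have the event prior to their index date will be included". Its formula likewise asks for no event in baseline. The following sentence leaves the length of the look-back to Table 3.

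The Table 3 footnotes in section 9.3 then fix that length:

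- Footnote 1, attached to peripheral neuropathy: "Incident cases have 30-day washout period applied".
- Footnote 2, attached to renal failure, hepatitis B and hepatitis C: "Incident cases have 60-day washout period applied".

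In Table 3 the event itself is a medical claim carrying a listed code in the period after index. Annex 2 gives the renal failure list as "ICD-10 Diagnosis: N17x, N18x, N19x, R34x, T82.4, Z49.02, Z99.2". The neuropathy list includes diabetic neuropathy codes (for example E11.40 and E11.42), the hepatitis B list includes B18.0 and B18.1, and the hepatitis C list includes B18.2.

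Inclusion criterion 4 (section 9.2.1) requires "At least 180 days of continuous closed-claims medical and pharmacy enrollment prior to index (inclusive) and 30 days post-index". Table 2 records baseline peripheral neuropathy, renal failure and any infection (including hepatitis B and C) from the myeloma diagnosis to the day before index.

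**The concern.** Chronic conditions need not be coded every month or two. A look-back of 30 or 60 days can miss established disease, and the next routine code after index then reads as onset. The baseline table could show a patient with renal failure or neuropathy while the safety table counts the same patient as a new case.

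Pre-existing disease is to be expected here. Section 7 names renal failure as a feature of myeloma and describes an approved population with at least four prior lines of therapy. The abstract names peripheral neuropathy among the adverse events of interest, yet it gets one of the shorter windows. No passage justifies the short windows for chronic codes, and section 9.9 does not list old disease counted as new among the limitations.

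**Working it through.** **Passages side by side.** The plan states no incidence figure or coding frequency, so there is no figure of its own to reproduce. The conflict is visible without a model. Kidney codes N18, N19 and Z99.2 fall under three look-backs:

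| Use | Look-back |
|---|---|
| Baseline renal failure (Table 2) | Myeloma diagnosis to day before index |
| Charlson renal disease item (Table 2) | 180 days before index |
| Incident renal failure (Table 3, footnote 2) | 60 days before index |

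The windows use 30/180 = 17% and 60/180 = 33% of the guaranteed look-back.

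**Illustration of size.** Assume that a pre-existing condition is coded as a Poisson process with mean gap g, at the same rate before and after index. A false incident case needs two things: no code in washout W, and at least one code in observation time F. Its share among pre-existing cases is

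m = exp(−W/g) × (1 − exp(−F/g)).

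Take g = 3 × 30.4375 = 91.3 days, using the month length from section 9.7.5.

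- First factor, no code in the washout: 0.720 at W = 30, 0.518 at W = 60, 0.139 at W = 180.
- Second factor, at least one code afterwards: 0.142 at F = 14, 0.627 at F = 90, 0.861 at F = 180.

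| F (days) | W = 30 | W = 60 | W = 180 |
|---|---|---|---|
| 180 | 62% | 45% | 12% |
| 90 | 45% | 32% | 9% |
| 14 | 10% | 7% | 2% |

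With F = 180 and g varied from 30 to 180 days, m runs from 37% to 62% at 30 days, 14% to 47% at 60 days, and 0.2% to 23% at 180 days. The longer window is better at every gap, but it does not remove the error.

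For scale only: section 9.5 gives 133 patients with an elranatamab claim, before eligibility is applied. If 30% had the condition already (assumed), then 133 × 0.30 × m at F = 180 gives about 25, 18 and 5 false incident cases for the three windows.

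**Net direction.** The formula in 9.7.6 divides by the total cohort. Let p be the share with pre-existing disease and i the true risk among the rest. The printed estimate is then (1 − p)i + pm, which differs from i by p(m − i). It is too high if m exceeds i and too low if m is below i. The documents give neither quantity.

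**The case against.** The strongest reply has four parts.

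- **Size.** No passage gives a coding frequency, and a constant coding rate through the start of treatment is unsupported. This stands: the percentages are illustrations. A reader might also take 72%, 52% and 14% (the chance of no code in 30, 60 and 180 days) as the error. That overstates it, because a code after index is also required, within a period ending 14 or 90 days after the last dose.
- **Direction.** A reader might infer that the reported incidence is biased upward. The documents do not establish this. The short washout adds to the numerator, but the total-cohort denominator lowers the percentage.
- **Remedy.** A 180-day washout for every listed outcome would be too blunt. The renal list mixes acute codes (N17x, R34x) with chronic ones, and a resolved acute episode five months earlier would stop a new acute event from counting. Anemia and hypogammaglobulinemia also carry footnote 1, but the case made here does not extend to them without further argument.
- **Importance.** The outcome is exploratory, the study makes no between-group comparisons, each event is also reported as prevalent, and 9.7.6 does not attribute events to the drug. All true. Hepatitis counts may also be small enough to be suppressed.

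None of this answers the classification error. Section 9.7.6 does defer to Table 3, so the short windows are what would be applied. They are stated numbers in the protocol, not details left open for the SAP.

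**Conclusion.** The point holds for peripheral neuropathy, renal failure and hepatitis B and C. As written, old disease that is uncoded in the washout and coded after index counts as incident, contrary to the intent of 9.7.6 and inconsistent with Table 2.

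Under a three-month coding gap and 180 days of observation, the affected share of pre-existing cases is about 62% with 30 days and 45% with 60 days, against 12% with 180 days, and less with shorter observation. These figures rest on the assumed Poisson coding and gap. The conflict between the passages does not.

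The consequence is an inflated incidence numerator in exploratory objective 1. Prevalence is unaffected, and the net direction of the reported percentage remains open while the denominator is the whole cohort. Neuropathy and renal failure carry most of the weight. The definition should be corrected before the final analysis; no primary objective is threatened.

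**What to change.** 1. For chronic codes in the neuropathy, renal failure and hepatitis B/C lists, replace the 30- and 60-day washouts with at least the guaranteed 180 days, or with all available history as in Table 2. Only the second option aligns the safety and baseline tables fully.
2. Split the renal list: acute codes (for example N17x, R34x) keep a short washout, and chronic codes (N18x, Z99.2) get the long one. Keep short washouts for other acute events.
3. Reword 9.7.6 so that its exclusion rule, the baseline term in its formula and the Table 3 footnotes name the same window, and make patients at risk the incidence denominator.

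The cost is an edit to Table 3, the code list and 9.7.6, with no new data. At-risk denominators will shrink, possibly noticeably for common conditions, and some cells may fall to between 1 and 10 patients and be suppressed under the CMS rule in section 9.4.

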9.4. Data Sources

This study will use Medicare FFS data from the VRDC, which represents 100% of the claims for all Medicare FFS beneficiaries in the US. The Medicare FFS data includes information on patient demographic and enrollment information, as well as inpatient, outpatient, and prescription drug claims. This source of insurance claims data encompasses comprehensive, longitudinal records detailing medical procedures, diagnoses, treatments, and associated costs within the healthcare system, as well as patient characteristics and outcomes such as race/ethnicity, zip code, and all-cause mortality records. The proposed data cut for this study spans from 2016 to December 2025. Data through September 2024, June 2025, and September 2025 will be used for interim analysis, with data through December 2025 to be used for the final analysis and for the final report.

The Medicare FFS data is subject to the CMS cell size suppression policy, which sets minimum thresholds for the display of CMS data. The policy stipulates that no cell (e.g., admissions, discharges, patients, services, etc.) containing a value of 1 to 10 can be reported directly. A value of zero does not violate the minimum cell size policy. The intent of this policy is to protect patient privacy and to protect any users of the data. The implication is that the analysis can extract data only in cases where the underlying cohort size is greater than ten patients. Distributions can still be reported, e.g., so long as a patient cohort volume is not displayed as less than 11. All insights derived from the CMS dataset are subject to export and approval processes administered and scheduled by CMS.

A strong advantage of the Medicare FFS database is its representation of all Medicare beneficiaries in the US and therefore is a comprehensive view of the population of patients over age 65. However, within the Medicare population there are unique dynamics such as dual eligible status, age less than 65 and Medicare Advantage plans. The Clarify Health team is skilled at minimizing the impact of these factors. Moreover, the Medicare population are likely to be more burdened by disease than a younger, commercially insured population. Therefore, controlling for comorbidities by using something like the Charlson Comorbidity Index, or matching patients, can allow for a more robust analysis.

In addition to the Medicare FFS data that Clarify has access to from the VRDC, we source and maintain a dataset of social determinants of health (SDoH) attributes which can be linked to the Medicare FFS data at the patient level. These attributes are not available for all beneficiaries but will be included where available. As an example, attributes that can be included in the analysis are household income, household education, among others. Clarify Health is the only analytics organization with approval to do so from CMS. These attributes are sourced from third party vendors such as credit agencies and advertising agencies and have undergone validation by Clarify Health prior to ensure they are suitable for analysis.

9.5. Study Size

As of August 2024, the dataset included 133 patients with a claim for elranatamab. To further assess whether sufficient sample size is available to proceed with the study, power analysis will be completed to assess estimates of precision for a one sample means considering either the elranatamab or teclistamab samples.

9.6. Data Management

This study will leverage Medicare FFS insurance claims data from the VRDC, representing 100% of the claims for all Medicare FFS beneficiaries in the United States. This system is securely managed by CMS and access is only provided to authorized users. An analytical dataset comprising all records required for planned analyses will be created from information contained exclusively within the Clarify Health database. The analytic file will include person-level data, and will include information on baseline characteristics, study measures, and health plan enrolment dates. Variables will be created based on information from healthcare claims and enrolment information, which will be linked at the person level. Data for this study will be processed and managed exclusively by Clarify Health.

9.7. Data Analysis

This study will be largely descriptive in nature, and no formal statistical comparisons will be performed between groups. All characteristics and outcomes will be reported separately for each cohort. The number of patients who meet study eligibility criteria will be summarized in an attrition table. Inclusion and exclusion criteria will be listed hierarchically and the number of patients remaining at each step will be reported. Patient and treatment characteristics will be summarized using descriptive statistics. Categorical variables will be summarized by the number of available observations, frequency, percentage, and 95% confidence limits. Continuous variables will be summarized by the number of available observations, mean, standard deviation, 95% confidence limits, median, quartiles, minimum, and maximum, where appropriate. The prevalence and incidence, as well as the associated 95% confidence intervals (CI) for each adverse event, will be estimated. Kaplan-Meier methods will be used to estimate the median time to event, including 95% CIs for TTNT/D and OS. All-cause HCRU and MM-related HCRU will be measured as the mean, SD, median, IQR, minimum, and maximum of the total number of IP, OP, ED, and pharmacy claims. Given the variable follow-up time available for each patient, HCRU and costs will be reported, for instance, on a per-patient-per-month (PPPM) basis. Relative Administration Intensity (RAI) will be calculated as the ratio of the actual number of administrations during each time period divided by the expected number of administrations based on the label for the treatment.

Based on the study cohorts of interest, patients may be characterized by the following attributes of interest:

- Demographic characteristics such as age, sex, race/ethnicity, state, and region
- Reason for Medicare enrollment
- Social determinants of health such as household income, education level, marital status, and home ownership

PFIZER CONFIDENTIAL

- Clinical characteristics such as comorbidity and past treatment status
- Healthcare resource utilization such as hospitalization and place of service distribution

Subgroup analysis will identify samples of patients based on reason for Medicare entitlement: disabled beneficiaries, beneficiaries with end-stage renal disease (ESRD), and beneficiaries aged 65 to 115 years qualifying by age.

Additional segmentations may be added if agreed upon by Pfizer and Clarify and documented appropriately in the study protocol. These attributes can be assessed during baseline, pre-index and/or post-index as deemed appropriate by the study team.

Detailed methodology for summary and statistical analyses of data collected in this study will be documented in a statistical analysis plan (SAP), which will be dated, filed, and maintained by the sponsor. The SAP may modify the plans outlined in the protocol; any major modifications of primary endpoint definitions or their analyses would be reflected in a protocol amendment.

